Digital (finger) ulcers are common in patients with systemic sclerosis (SSc) otherwise known as scleroderma and many of the current treatments used can cause side effects or are not effective. We want to investigate a novel light-based therapy to potentially treat digital ischaemia (low blood flow) that causes digital ulcers.

In our previous study, our custom-built light-based treatment device, consisting of red, infrared, and violet wavelengths was found to be safe and feasible. There were also some early signals of potential benefit for digital ulcers in patients with SSc. To take this treatment approach forward, we now need to refine the optimal 'dose' of light.

Participants wishing to take part will need to attend Salford Royal Hospital for three study visits. At the first visit the research team we will examine the participant's fingers and back of their hands for any skin thickness changes (gently pinching the skin) as is routinely performed in the scleroderma outpatient clinic. Skin thickness will also be measured at these sites using an ultrasound machine.

At each visit, participants will receive one of three randomised 'doses' of the combination light therapy. The research team wishes to understand how the skin (blood flow and temperature) reacts to increasing dose of light. All patients will receive the three 'doses' of light over the three study visits (but not all in the same order), there is no placebo treatment. The light application to the skin will take approximately 15 minutes to complete.

We will measure the blood flow and temperature of the skin immediately before, directly after, and then every 10 minutes for 90 minutes after the light therapy. These will be measured using a type of scanner called 'laser Doppler imaging' and a thermal camera, which will each take approximately 1 minute (or less) per scan.

3 Background

Systemic sclerosis (SSc) is a complex autoimmune connective tissue disease characterised by microvascular abnormalities, fibrosis of the skin and internal organs, and immune system activation [1]. Digital ulcers (DUs) are common in patients with SSc and are responsible for much of the pain and disability associated with the disease [2,3].

SSc-Digital Ulcers (DUs)

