Our previous feasibility study demonstrated that our novel LTTT for DUs was safe, feasible, and well tolerated. Furthermore, there was an early tentative suggestion of treatment efficacy. There is a significant therapeutic rationale to develop locally acting treatments for SSc-DU, which likely would be better tolerated by patients, and could be administered potentially in the community (our outpatient setting under medical supervision), thereby avoiding the costs and inconvenience from inpatient hospitalisation. Furthermore, many previous studies have found comparable efficacy at lower doses (total dose 5 to 10 J/cm²). Although, some studies have also found positive results with much higher doses, such as 20J/cm², 70J/cm², or even higher.

However, a biphasic response to light is well known, and therefore there is a need to scientifically determine the dose-ranging of LLLT for SSc-DU, including examination of potential patient- and disease-related factors.

4 Objectives

Primary Objective: To assess the safety, tolerability, and efficacy (as assessed by surrogate measurement of skin perfusion and temperature) of our LLLT (combined red, infrared and violet wavelengths) concerning dose finding with lower and higher irradiances, including evidence of a biphasic response with higher irradiance dose.

Secondary Objective: To investigate potential SSc patient- and disease-related factors relevant to cutaneous irradiation with LTTT.

- Age and disease duration.
- Skin thickness.

5 Study Design

A physiological, clinical laboratory-based, study of LLLT.

LTTT experimental setup

A new LTTT device (Figure 2) shall be constructed in-house by Medical Physics at Salford Royal Hospital and subject to appropriate safety and quality assurance checks.

Allocation of LLLT intervention

Prior to the initial study visit, an independent member of the study team shall perform the randomisation procedure. Randomisation to be done in house by study team (e.g., using random number generator/excel). All patients shall receive combined sequential red (810nm)/infrared (850nm) followed by blue (410nm) wavelengths. The dose per visit shall be dose-escalated in a pre-determined randomised order over the course of the three study visits: 5 J/cm² or 10 J/cm² (i.e., the dose of our previously explored LLLT), and 20 J/cm²

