Participants will not be paid to take part in the study; however, they will be reimbursed reasonable travelling expenses for each of their 3 study visits

[figure not shown]

Figure 3. Participant progression throughout the study. We assume no significant therapeutic carry over effect between the LLLT irradiation between study visits (minimum of 24 hours).

Preparation

Patients will be asked to abstain from caffeine-containing drinks and from smoking for at least 4 hours prior to study.

Clinical data

After signing the informed consent form, the patient will be interviewed by a member of the study team using a standard proforma and/or standardised proformas.

This will include:

- Demographic information.
- Gender.
- Age.
- Smoking status
- Fitzpatrick skin type/colour (for potential effects of melanin).
- Modified Rodnan skin score assessment
- Current medication/s.
- Past medical history.
- Disease-related history (e.g., history of severe digital vascular disease).
- Record of ulcers present and past and also of location, duration etc.
- Handedness (i.e., dominant hand).

Application of the LLLT device

We will apply the LLLT (for all study visits) to the dominant hand unless there are specific reasons not to, which will be documented. For example, due to patient preference or major musculoskeletal involvement with upper limb disability/contractures prohibiting correct positioning for the application of the LLLT.

Both the patient and device operator/s will wear appropriate safety goggles (as advised by Medical Physics at Salford Care Royal Hospital) at all times whilst the LLLT device is in operation. The patient will place their hand within the treatment area of the light-based device (total treatment area of approximately 15cm²), aiming to centralise the hand (fingers/thumbs and dorsal aspect) within the treatment region. The device will be directly controlled by an attached custom-built computer interface. At each study visit, the device will undergo a period of automatic calibration before use.

Using the custom interface/s, the dose of the wavelengths can be selected to be delivered as prior study. The dose will be delivered either at 5 J/cm², 10 J/cm² or 20 J/cm² based upon the patient study visit sequence/randomisation. The LLLT will take approximately 10-15 minutes to complete.

Outcome measures

Assessment of safety and tolerability

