At each treatment study visit any safety issues (between visits) will be documented (e.g., new concerns about cutaneous changes). This will be documented on a separate safety CRF at visits 2 and 3 (attached with this application). Patient reported pain on a VAS scale (0-100, where 100 is the most severe pain imaginable by

the patient) directly attributed to the LLLT will be recorded immediately after treatment, on a separate tolerability CRF at visits 1, 2 and 3 (attached with this application), to assess tolerability, at each study visit.

Assessment of efficacy

Laser Doppler imaging (LDI); LDI which measures blood flow allows a perfusion map (in arbitrary units) to be produced of the studied area. We will perform LDI immediately before and after the light exposures and then every 10 minutes for 90 minutes. LDI will include all the digits (thumb and four fingers) and dorsum of both the *treated* and *untreated* hands. Bilateral (matching) standard regions of interest (ROI) shall be assessed on the treated and untreated hands all LDI time points. The rationale of imaging these sites is to demonstrate an objective *localised* increase in skin perfusion with light treatment, and whether this differs between the digits and dorsum of the hand.

Thermography: Thermographic assessment measures skin temperature and provides an indirect measure of small and large blood vessel function and can also be applied to SSc-DUs. Standardised thermographic images shall be acquired immediately before and after the light exposures, and then every 10 minutes for 90 minutes. As for LDI, thermography will simultaneously image the whole treated hand to capture the fingers and dorsal aspect, and with contralateral counterparts on the untreated hand.

Assessment of persistent cutaneous digital ischaemia

Taken from the hand original acquired LDI and thermography images (as above), for any digital (finger) ulcers (DU) or pitting scars (DPS) present, perfusion measurements will be assessed at the lesion center (DU/DPS 'core') and immediately adjacent tissue (DU/DPS 'periphery').

Assessment of digital skin fibrosis:

Rodnan skin score: By a trained assessor using the modified Rodnan skin score by manual palpation (0-3 score, where 0 is normal and 3 is severe skin fibrosis/sclerosis).

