7.2 Statistical Analyses

To assess tolerability of irradiance wavelengths, VAS scores will be graphically explored. To observe the change over time, area under the curve will be calculated for each patient to estimate the blood flow/temperature, and a t-test will be used to test for differences. Our physiological study data shall inform the sample size calculation of a future feasibility RCT. However, in our previous investigation, which included eight patients (with 14 SSc-DU), we observed

an increase in perfusion of 15-32% post-irradiation with LTTT. We shall perform tentative analyses to explore the impact of our specified patient- and disease-related factors.

The study team including [name], [name], [name] and [name], will be responsible for transcribing, coding, de-identifying, storing/transferring, accessing and archiving study data.

8 Regulatory and Ethical Considerations

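### The only named efficacy test is an unspecified t-test on AUC, with no dose-response contrast for a three-dose, three-visit within-patient study whose primary objective includes a biphasic response

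*Protocol*

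**What the plan says.** **Analysis.** Section 7.2 gives the efficacy analysis in one sentence: "area under the curve will be calculated for each patient to estimate the blood flow/temperature", and then "a t-test will be used to test for differences". Pain scores are to be explored by graph. Patient and disease factors get tentative analyses with no method named.

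**Design.** The Lay Summary states: "All patients will receive the three 'doses' of light over the three study visits (but not all in the same order". Section 5, under allocation, adds: "The dose per visit shall be dose-escalated in a pre-determined randomised order over the course of the three study visits". Under application of the device it says: "The dose will be delivered either at 5 J/cm², 10 J/cm² or 20 J/cm² based upon the patient study visit sequence/randomisation". The caption of Figure 3 reads: "We assume no significant therapeutic carry over effect between the LLLT irradiation between study visits (minimum of 24 hours". Section 5 also brings in a second within-patient factor: "LDI will include all the digits (thumb and four fingers) and dorsum of both the *treated* and *untreated* hands".

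**Objective.** Section 4 makes dose finding with lower and higher irradiances part of the primary objective, "including evidence of a biphasic response with higher irradiance dose". Section 3 gives the biphasic response to light as the reason why a dose-ranging study is needed.

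**Size.** Section 6 plans twenty patients. The protocol states no significance level, power, SD, target difference between doses or within-patient correlation.

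**The concern.** A t-test compares two means, or one mean difference with zero. This design yields three correlated responses per patient, one for each dose, and visit is a further design factor. The sentence in Section 7.2 leaves open:

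- which of the three doses, two hands or several time points are set against each other;
- whether the comparison is within or between patients;
- whether the AUC is one value per dose visit, since it is described only as being per patient.

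Nothing in the sentence corresponds to the biphasic question, which concerns all three doses jointly: does the response rise and then fall?

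At stake is whether twenty patients can give a usable answer on dose. An analyst who follows Section 7.2 literally could run several unadjusted pairwise tests and read a dose-response shape from which p-values fall below 0.05. An analyst who took the test to be unpaired would also lose most of the advantage of the within-patient design. The results are meant to inform the sample size of a later trial, so a poorly estimated dose comparison would carry forward.

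**Working it through.** **There is no stated calculation to reproduce.** The protocol gives N = 20 without the other inputs, so the figures below show the size of the issue under assumptions.

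**Inputs from the protocol:** 20 patients, three doses each, and a t-test as the only named test.

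**Assumptions not in the protocol:** two-sided 0.05, normal data, total SD 1, no visit effect, no missing visits, within-patient correlation ρ of 0.5, 0.7 or 0.8, and a response at 10 J/cm² that is 0.5 SD above both 5 and 20 J/cm².

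**Step 1: one pair of doses, paired.** The variance of a within-patient difference is 2(1−ρ). The non-centrality is 0.5 × √20 / √(2(1−ρ)), on 19 degrees of freedom.

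**Step 2: one quadratic contrast.** For each patient take the response at 10 minus the mean of the responses at 5 and 20. Its variance is (1 + 0.25 + 0.25)(1−ρ) = 1.5(1−ρ), and its expected value is 0.5. The non-centrality is 0.5 × √20 / √(1.5(1−ρ)), which is √(2/1.5) = 1.15 times that of a single pair.

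**Step 3: peak shown by two paired tests.** Both 10 versus 5 and 10 versus 20 must be significant (by simulation).

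**Step 4: the test run unpaired.** The test uses the standard error √(2/20) = 0.316 whatever ρ is, whereas the true one is √(2(1−ρ)/20), or 0.224 at ρ = 0.5. The test is therefore too conservative. Simulated true alpha is 0.8% at ρ = 0.5 and 0.1% at ρ = 0.7.

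| | ρ = 0.5 | ρ = 0.7 | ρ = 0.8 |
|---|---|---|---|
| Non-centrality, one pair | 2.24 | 2.89 | 3.54 |
| Power, one pair, paired | 57% | 78% | 92% |
| Power, one pair, unpaired | 29% | 25% | 22% |
| Power, two paired tests both significant | 40% | 66% | 86% |
| Non-centrality, quadratic contrast | 2.58 | 3.33 | 4.08 |
| Power, quadratic contrast | 69% | 89% | 97% |

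**Step 5: false positives.** With no dose effect, three independent tests at 0.05 would give 1 − 0.95³ = 14.3%. The three paired comparisons share dose means, and simulation gives about 12 to 13%. The single quadratic contrast stays at about 5%.

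**Step 6: what a biphasic claim must require.** The quadratic contrast tests curvature, and a plateau between 10 and 20 J/cm² also produces curvature. A claim of a downturn therefore needs the 20-minus-10 difference as well. The signs of the two estimates are not enough. The contrast vectors (−1, 2, −1) and (0, 1, −1) have correlation 3/√(6×2) = 0.866. With no dose effect at all, both estimates then point to a downturn with probability 1/4 + 60/360 = 0.417, about 42% of the time. Both confidence intervals have to exclude zero.

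**The case against.** **T-tests can answer the question.** A fall from 10 to 20 J/cm² is a two-mean comparison, and a one-sample t-test on each patient's quadratic contrast tests curvature directly. This stands. A reader might infer that the named method cannot address the biphasic objective, and that goes too far. The plan states no such contrast, and the pairwise route has less power.

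**Pairing may be left to a statistical analysis plan.** This stands in part. Section 7.2 says neither paired nor unpaired, so a reader who concludes that the pairing is handled wrongly has read silence as error. The unpaired figures show what that reading would cost, not what the investigators intend. The wider point survives because the protocol does fix a method, and a later plan written to Section 7.2 would inherit it.

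**Visit effects are limited.** Dose order is randomised, visits are in the morning in a laboratory at 23°C, and caffeine and smoking are restricted beforehand. This guards against systematic bias but does not replace a visit term. The balance of sequences is not stated, and 20 does not divide evenly into three orders (6.67 each) or six (3.33 each). No size for a visit effect can be taken from the protocol, so none is claimed.

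**Multiplicity matters less in a small physiological study.** This is fair. One could multiply dose pairs by imaging methods and by sites and infer a large familywise error. Section 7.2 does not give a number of tests, and images of the same hand are not independent. Only the figure for three dose pairs on one outcome is used here.

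**Missing visits.** Section 6.5 keeps the data of withdrawn patients, and with paired tests a patient who misses one visit still contributes to one pair. The loss is partial.

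**Conclusion.** The point holds in a limited form. Section 7.2 commits the study to a single unspecified t-test as its only inferential method, and that does not match a randomised-order, three-dose, within-patient design or the dose-finding part of the primary objective.

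Across ρ from 0.5 to 0.8, the efficiency lost by pairwise paired testing is the gap between 40 to 86% and 69 to 97% power. The two criteria are not identical, since the second detects curvature and not by itself a downturn. If the test were run unpaired, power for one 0.5 SD dose difference would be about 29 to 22%, against 57 to 92% paired.

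These figures rest on the assumed correlation, the 0.5 SD peak at the middle dose, normality and no visit effect. None of these is given in the protocol. The mismatch between the test and the objective does not depend on them.

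**What to change.** Rewrite the efficacy part of Section 7.2 as follows:

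1. Calculate one AUC per patient per dose visit for each outcome.
2. Analyse each outcome with a linear mixed model, with dose (three levels) and visit (three levels) as fixed effects and patient as a random effect, using all available visits.
3. Pre-specify a linear contrast (−1, 0, 1) and a quadratic contrast (1, −2, 1) over 5, 10 and 20 J/cm². Each dose doubles the one before, so the three are equally spaced on the log2 scale. Add the 20-minus-10 difference. Report each with a 95% confidence interval.
4. Name one lead outcome and make the others supportive.
5. Claim a biphasic response only if the confidence intervals for the quadratic contrast and for the 20-minus-10 difference both lie wholly below zero. Otherwise report the estimates and intervals without claiming a downturn.

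The cost is wording and slightly more analysis work, with no new patients or measurements. The claim also becomes stricter. Because it requires the 20-minus-10 difference to be significant, its power under the assumptions above cannot exceed that of this single comparison, about 57%, 78% and 92% at ρ = 0.5, 0.7 and 0.8 if it is tested as a paired difference. With twenty patients, a real downturn may therefore be reported only as an estimate with its interval.

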8.1 Study Conduct

- The study will be conducted in accordance with the UK Policy Framework for Health and Social Care Research and other applicable guidance.
- The study will not commence until all regulatory approvals are in place, which will include HRA Approval, REC Approval and confirmation from local R&I that the Trust has capacity and capability to carry out the research.
- All amendments will be submitted to HRA and/or REC by the sponsor and disseminated to sites as applicable.

8.2 Monitoring and Audit

- The study will be subject to the standard procedures for monitoring and auditing of studies by the sponsor.
- Any changes to the protocol will be agreed with the sponsor prior to submission to HRA and/or REC for review, with the exception of where urgent safety measures apply.
- All staff working in the study will have completed appropriate training to undertake the duties delegated to them by the Principal Investigator such an ICH-GCP and local SOP training.

8.3 **Protocol Deviations**

- A records of all protocol deviations should be maintained within the ISF.
- Any major deviations to the protocol will be reported to the sponsor within 24 hours of the occurrence to allow an impact assessment to be completed.
- Consideration will be given to the nature of the reported deviation, its causes, and the potential impact on the study.
- Where necessary, a deviation from the protocol may lead to an amendment to the protocol

8.4 Stopping Rules

It is not anticipated that the study will be stopped prior to its intended end-date. However, the study will be halted if:

- New information comes to light which means that the aims of the study are futile.
- Safety issues come to light regarding the intervention.
- Resources to conduct the study are no longer available.

Short title/acronym: Light treatment for scleroderma finger ulcers - study 2

8.5 Data Protection and Patient Confidentiality

Patient confidentiality will be maintained, and the study will be compliant with the requirements of the Data Protection Act 2018 in the following ways:

- The creation of coded, depersonalised data where the participant's identifying information is replaced by an unrelated sequence of characters.
- Secure maintenance of the data and the linking code in separate locations using encrypted digital files within password protected folders and storage media.
- Limiting access to the minimum number of individuals necessary for quality control, audit, and analysis.
- [name] will act as the data custodian for the study data.
- The data will be stored until the final publication, after which time it will archived by Northern Care Alliance NHS Foundation Trust for 25 years from the date of the final publication.

Electronic patient records will be accessed by members of the direct care team in order to obtain patient's addresses and telephone numbers for recruitment purposes. The identification and screening of potential participants will be done by direct care team. This may include (where appropriate) sending letters to patients with the PIS. Once consent has been given, medical records may be accessed by either direct care team or research team to access study data.

Study data will be pseudonymised, having a study ID number that is linked to a study participant. Pseudonymised study data will be stored electronically on Trust or University of Manchester computers, and manually in locked filing cabinets. The details that link the study ID number to a study participant will be stored separately on password protected Trust computers alone.

Study data and material may be looked at by individuals from the University of Manchester, from regulatory authorities or from the NHS trust, for monitoring and auditing purposes, and this may well include access to personal information.

Electronic personal data will be stored on NHS computers which are encrypted, and password protected. Electronic pseudonymised data will be stored on the University of Manchester computers.

Paper based Case Report Forms (CRFs) will not contain participant identifiable data. Instead a study ID will be assigned to participants to ensure no identifiable data is available. It will be the responsibility of the local Principal Investigator (PI) to ensure the physical security of the CRF/research data during the trial.

All confidential data will be kept in a locked file room and electronic data will be password protected where only the Investigator and delegated staff have access.

After consent is obtained, patients will be given a unique code that will be used for data acquisition and analysis.

Pseudonymised data will be analysed on NHS or University computers by members of the research team.

Statistical advice/support will be provided by Research & Innovation, Northern Care Alliance NHS Foundation Trust, [name].

